A physician Investigator will approach the surrogate using the same process as outlined in obtaining consent for all subjects. The study will be explained in full to the surrogate, including the purpose of the research, procedures, risks and benefits, right to withdraw, alternative care and confidentiality. We will ensure and document that the surrogate understands that his/her decisions should be based on substituted judgment. If a potential subject did not previously express a view, the surrogate should make the decision based on the potential subject's best interests. We will explain the difference between standard of care and research.

If surrogate consent is obtained, the basis of the determination of the subject's lack of capacity will be documented in the research records, along with a description of the relationship of the surrogate.

After consent is signed, subjects in the prospective interventional cohort will be assigned to receive either the Impella RP or ProtekDuo, as indicated by the treating physician. The RVAD will be placed within 48 hours preoperatively of the LVAD implantation, at the time of LVAD implant, or immediately following the implant. The RVAD will be left for up to 72 hours. RVAD management will be performed according to MGH standard of care by the medical staff.

There will be no consent process for the historical control cohort as there are no interventions for this group. The clinical data required for this study is already collected in a secure database per standard of care.

VI. STUDY PROCEDURES

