All LVAD candidates at Massachusetts General Hospital (MGH) will be screened for trial eligibility. Every eligible candidate will be asked to participate. Subjects who consent to the study will undergo pre-operative or intra-operative placement of an RVAD, which will be left in up to 72 hours postoperatively. If it is determined that a subject requires support for longer than 72 hours, the treating physician will consider utilizing a more durable form of right ventricular support (CentriMag paracorporeal RVAD requiring direct cannulation), as is standard practice. The type of RVAD (Impella RP or ProtekDuo) inserted will be determined by patient needs and venous access and will be up to the discretion of the treating physician. The use of the ProtekDuo will be prioritized due to the benefit of the jugular approach in device placement, which does not limit patient mobility. If there is no jugular access, the Impella RP, which is placed through a femoral approach, will be used. We aim to enroll 25 subjects in the prospective interventional cohort, and compare to 25 subjects in the matched retrospective control cohort.

All enrolled patients in the prospective interventional cohort will undergo surgical placement of a percutaneous RVAD within 48 hours preoperatively to LVAD implantation, at the time of LVAD implant, or immediately following the implant. After removal of the RVAD, subjects will receive standard treatment according to MGH's standard of care. Data will be obtained for subjects in both cohorts from the electronic medical record in EPIC at MGH and will be reviewed throughout the study through the 1-year follow-up period. Other standard of care tests are administered regularly at LVAD follow-up visits, including: the KCCQ-12 and EQ-5D surveys, a neurocognitive trailmaking test, and a six-minute walk and gait speed test. These are collected per standard of care at the following timepoints: pre-implant, 3 month (+/- 30 days), 6 month (+/- 60 days), and 1 year (+/- 60 days). These results will also be collected and entered to the study database.

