The primary analysis will be performed in an intention-to-treat fashion using a two-sided T-test (alpha level=0.05). The null hypothesis is that the mean maximal 24-hour VIS will not differ between intervention and historical groups. The alternate hypothesis is that compared to standard of care (historical cohort), placement of an RVAD within 48 hours before or during LVAD implantation will decrease the mean maximal 24-hour VIS score by 50%. Analysis assumptions will include independence of study groups and lognormal (or normal) distribution of data in each group.

SECONDARY OUTCOMES

Secondary end points will include:

- Total VIS (throughout hospitalization)
- ICU length of stay (LOS)
- Total post-operative LOS after LVAD implantation
- Survival at discharge after LVAD placement
- Survival at 1 year after LVAD placement or heart transplant
- End organ dysfunction including
 - o Development of acute kidney injury (AKI) – defined as increase in serum creatinine (sCr) to 4mg/dl or greater, a 150% or greater increase in sCr over the baseline preoperative value, or a new requirement for renal replacement therapy
 - o Liver dysfunction
- LVAD device speed

Cox proportional hazard models (one sided, 0.05 significance level) will be used to compare rates of secondary outcomes between intervention and historical arms. Event rates and relative risks will also be estimated for each of these outcomes.

POWER ANALYSIS

Sample size calculations are estimated based on expected effect size, which was determined based on expert consensus (reduction in the mean maximal 24-hour VIS score by 50% in the intervention arm compared to the historical controls). 80% power will be generated with 2-tailed confidence interval of 0.05 from a sample size of 34 patients (17 per group). Estimating a

standard deviation of 0.5 of the outcome in the population and 20% attrition and/or cross-over, investigators anticipate that 20 patients will be needed to test this hypothesis. This power estimation assumes a lognormal distribution of the data. We plan to allow for 25 patients to participate in the prospective arm of the study to allow for incorrect assumptions.

IX. RISKS AND DISCOMFORTS

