We will perform an interim safety/outcomes analysis after the first 10 subjects have been enrolled to ensure that the anticipated risk/benefit assessment remains unchanged. The report will be made available to the IRB in a timely manner. If this analysis shows that 10 subjects provide enough data to draw significant conclusions, enrollment will be stopped and the study will be concluded. If other assumptions prove to be wrong and additional patients will be needed, this will be carefully considered and communicated to the IRB prior to proceeding.

XII. REFERENCES

5. Na, S. J., Chung, C. R., et. Al. (2018). Vasoactive Inotropic Score As A Predictor Of Mortality In Adult Patients With Cardiogenic Shock. *Journal of the American College of Cardiology*, 71(11). doi: 10.1016/s0735-1097(18)31355-x

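### The 10-subject outcomes look may lead to more enrolment with no stated trigger or maximum, while the final test stays a plain 0.05 t-test, so 5% is not guaranteed

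*Protocol*

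**What the plan says.** Section XI (Monitoring and Quality Assurance) schedules one interim look at safety and outcomes once 10 subjects are enrolled. Two decisions follow from it. Enrolment ends if those subjects already allow a significant conclusion. In the other direction, the section reads "If other assumptions prove to be wrong and additional patients will be needed", and the only condition attached is that the matter is weighed and the IRB informed before going on. No trigger, maximum or change to the analysis is given.

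Section VIII (Primary Endpoint) fixes the primary analysis as "two-sided T-test (alpha level=0.05", with no allowance for the look. The Power Analysis in the same section lists the assumptions. The first is the effect, a "reduction in the mean maximal 24-hour VIS score by 50% in the intervention arm compared to the historical controls", which rests on expert consensus. The next are a "standard deviation of 0.5 of the outcome in the population and 20% attrition and/or cross-over", together with a lognormal distribution.

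On size, section VI says: "We aim to enroll 25 subjects in the prospective interventional cohort, and compare to 25 subjects in the matched retrospective control cohort". On the controls, section V says: "The clinical data required for this study is already collected in a secure database per standard of care". The treated-control difference can therefore be computed at the look.

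**The concern.** Whether an ordinary t-test survives a mid-trial increase in size depends on what prompted the increase. An increase prompted by the SD or by attrition barely touches the false-positive rate. An increase prompted by a disappointing treated-control difference gives the weakest interim results a second chance and leaves the strongest ones alone, which pushes the error above 5%.

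The protocol does not say which kind it means. The 50% effect is one of the listed assumptions, so the wording covers the harmful kind as well as the harmless one. This is the trial's only primary test, and a reader of the result could not tell from the protocol whether the nominal 5% applies.

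**Working it through.** **Step 1: the protocol's own figure.** Section VIII states that "80% power will be generated with 2-tailed confidence interval of 0.05 from a sample size of 34 patients (17 per group". With difference 0.5 and SD 0.5, the standardised effect is 1.0. The normal approximation gives n = 2 × (1.960 + 0.842)² / 1.0² = 15.7, so 16 per group. The t-test solution is 16.7, so 17 per group, with power 0.807. The figure reproduces, but only with 50% entered as 0.5 on the scale of the SD. As ln 2 on the log scale, the t-test solution is 9.2, so 10 per group.

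**Step 2: why the trigger matters.** Let z₁ be the standardised difference at 10 v 10, n the final size per arm and f = 10/n. With no true effect, the chance of a significant final test given z₁ is

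P(z₁, n) = 1 − Φ[(1.96 − √f·z₁)/√(1−f)] + Φ[(−1.96 − √f·z₁)/√(1−f)].

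- z₁ = 0: n = 25 gives 2 × [1 − Φ(1.96/√0.6)] = 1.1%. n = 50 gives 2 × [1 − Φ(1.96/√0.8)] = 2.8%.
- z₁ = 1.5: n = 25 gives 9.6%. n = 50 gives 7.6%.

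Extending when the look is flat raises the false-positive chance. Extending when it is moderately promising lowers it.

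**Step 3: overall error.** The protocol gives a first look at 10, a planned 25 v 25 and a two-sided t-test at 0.05. The extension rules below are assumptions, because the protocol states none. *Re-sized on effect* means n = 2 × (2.802/d)², with d the observed difference in SD units, held between 25 and a cap. Results are from simulation under no true effect (60,000 to 400,000 runs), with no early stop unless shown.

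| Rule after the look | Type I error |
|---|---|
| Single test at 25 v 25 | 5.0% |
| Re-sized on SD only | about 5.0-5.4% |
| Extend to 35-100 per arm whenever the look is not significant | 5.3-5.8% |
| Re-sized on effect, look 10 v 10, both arms grow, caps 50-100 | 5.7-6.4% |
| Re-sized on effect, look 10 v all 25 controls, both arms grow, caps 50-100 | 6.0-6.8% |
| Re-sized on effect, look 10 v 10, only the treated arm grows, caps 50-100 | about 5.5-5.8% |
| Extend only if the observed effect is 0.3-1.0 SD | 4.4-4.8% |
| Early stop at p < 0.05, no extension | 8.7% (10 v 10), 8.0% (10 v 25) |
| Early stop, then re-sized on effect, look 10 v 10, both arms grow, caps 50-100 | 9.6-10.1% |

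**Step 4: upper limit for the extension alone.** Choosing, for each z₁, the n that maximises P(z₁, n) and averaging over z₁ gives 6.0% (cap 50), 6.5% (cap 100) and 7.0% (cap 1000). This limit is for a look at 10 v 10 under the normal approximation. It does not bound the 10 v 25 look.

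**Step 5: the remedy.** An inverse-normal combination with squared weights 10/25 = 0.4 and 15/25 = 0.6, separate controls in each stage and the same effect-based re-sizing gives 5.0% at caps of 50, 60 and 100.

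**The case against.** The strongest defence is that the sentence is a notice, not a rule. Any increase would go to the IRB first, and size and analysis could both be revised then. The word *other* follows a sentence about conclusions from the outcome, so it may point to the remaining inputs: SD, attrition and distribution. On that reading the error stays near 5%. A statistical analysis plan that is not shown might also settle the matter. Even on the adverse reading the excess is small, and one plausible trigger (0.3-1.0 SD) takes the error below 5%.

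Much of this stands. The nuisance-only reading is fair, and the excess is modest. But nothing in the text requires that reading, and the effect is the first assumption in the power paragraph. Telling the IRB does not protect an error rate. The protocol itself both grants the open permission and names the unadjusted test, so this is not just detail left to another document. That the result can fall on either side of 5% shows that the rule has to be written down.

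A reader might go further and infer that the protocol makes a small effect the reason to extend, or that the extension by itself breaks the 5% level. The text does not say the first, and the second is true only under some triggers. Nor can one say that a reported 50% reduction is biased: the 50% is a hypothesis, and no bias was calculated here.

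**Conclusion.** The point holds in a limited form. As written, the two-sided 5% level is not guaranteed, which is weaker than saying that it is lost. An effect-driven increase costs about 0.5 to 1.8 percentage points (5.5-6.8%), given re-sizing to 80% power on the observed effect, a floor of 25 and caps of 50-100 per arm. An increase driven by the SD costs almost nothing, and the same is expected for attrition that is unrelated to the outcome.

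The extension is the smaller of the two problems in that paragraph of section XI. The unadjusted early stop, if significant means p < 0.05, alone gives about 8-9%. The two together reach about 9-10%. A boundary for the early stop would still leave the extension without a rule, so both sentences need attention.

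**What to change.** Replace the extension sentence in section XI with wording such as: *Enrolment may be increased after the 10-subject look only if the within-group SD of log maximal 24-hour VIS, or the attrition, differs from the value assumed in section VIII. It will not be increased because of the observed treated-control difference, and it will not exceed [stated maximum] per cohort.* Section VIII should then say on which scale the SD of 0.5 is meant, since the trigger depends on it.

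If the sponsor wants to be able to extend on the effect, replace the plain t-test with a pre-specified inverse-normal combination test. Use squared weights 0.4 and 0.6 (weights √0.4 = 0.632 and √0.6 = 0.775), and split the controls between the stages in advance. Without that split the stages share controls and are not independent.

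The early-stop sentence needs its own boundary. For looks at 40% and 100% of the information, nominal p < 0.0283 at both looks (Pocock type), or p < 0.0019 and then p < 0.0492 (O'Brien-Fleming type), holds two-sided 0.05.

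The cost is a few sentences and no new data. The downside is small: the sponsor gives up extending because the effect looks small, or must use a weighted test.
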